- SF-VAQ measured at baseline and every 3 months during the follow-up period. The Short-Form Vascular Access Questionnaire (SF-VAQ) was developed to measure hemodialysis patients' satisfaction with their vascular access (31). The questionnaire contains 13 items (7-point Likert scale) in 4 domains (overall satisfaction, physical symptoms, social functioning and complications), and has a single summary score.

- EQ-5D-5L measured at baseline and every 3 months during the follow-up period. The EQ-5D-5L was developed to measure health-state utility values. The questionnaire contains self-classifiers at 5 levels in 5 dimensions (mobility, self-care, usual activities, pain/discomfort and anxiety/depression) (32). Utility values will be calculated from these health states using preferences elicited from the Dutch general population (36). Quality-adjusted life years will be calculated with these utility values using the area under the curve method.

6. Quality of the surveillance program

- Repeatability and reproducibility of vascular access flow volume measurements (mL/min) using ultrasound dilution in routine clinical practice.
- Diagnostic accuracy of vascular access flow volume measurements to predict clinical signs of flow dysfunction and access thrombosis within 1 month in the intervention group. Diagnostic accuracy will be reported as sensitivity, specificity, negative predictive value, and positive predictive value.
- The percentage of vascular access balloon angioplasties that have resulted in technical success (residual stenosis <30%) and clinical success (increase in flow volume to >500mL/min, restoration of vascular access function and resolution of any clinical signs of flow dysfunction).
- Vascular access primary, primary assisted, and secondary patency after balloon angioplasty (time to event).
- Adherence (in %) to the vascular access follow-up protocol and to the study protocol for referral to correct vascular access stenosis.

7. Other outcome measures will be registered for explanatory analyses and are defined according to the ESVS guidelines on vascular access (1):

- Primary patency of vascular access (intervention-free vascular access survival): the interval (in days) between randomization and the first intervention for vascular access dysfunction or thrombosis or its abandonment.

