Problem on dialysis
Access care
Hospitalization
Worry about access longevity

Include only questionnaires with complete data. Questions are Likert scores from 1 to 7. Domain scores are the sum of the 4 questions. The total score is the sum of the 3 domains.

Sensitivity analysis: exclude patients with interventions on the current vascular access before enrollment

Statistical analysis: mixed linear model

Table 5C: Change in SF-VAQ scores with access-related interventions

	Before intervention (>30 days)	Around intervention (30 days before – 90 days after)	P	Clinically relevant change
Total score	Mean (SD)	Mean (SD)	...	%
Physical domain	Mean (SD)	Mean (SD)	...	%
Pain	Mean (SD)	Mean (SD)	...	
Bleeding	Mean (SD)	Mean (SD)	...	
Swelling	Mean (SD)	Mean (SD)	...	
Bruising	Mean (SD)	Mean (SD)	...	
Social functioning domain	Mean (SD)	Mean (SD)	...	%
Daily activities	Mean (SD)	Mean (SD)	...	
Appearance	Mean (SD)	Mean (SD)	...	
Sleep	Mean (SD)	Mean (SD)	...	
Bathing and showering	Mean (SD)	Mean (SD)	...	
Dialysis complications domain	Mean (SD)	Mean (SD)	...	%
Problem on dialysis	Mean (SD)	Mean (SD)	...	
Access care	Mean (SD)	Mean (SD)	...	
Hospitalization	Mean (SD)	Mean (SD)	...	
Worry about access longevity	Mean (SD)	Mean (SD)	...	

Compare SF-VAQ scores before (latest but >30 days before) and around (closest to the intervention but <30 days before and <90 days after) the access-related intervention. Calculate the proportion of patients with a clinically relevant change in SF-VAQ scores.

The clinically relevant change in SF-VAQ scores is defined as 0.5 times the standard deviation of the difference in SF-VAQ scores between two adjacent measurements in patients without vascular access-related interventions or vascular access-related (serious) adverse events.

Statistical analysis: paired Student t-test

Table 5D: Change in SF-VAQ scores with thrombosis

	Before thrombosis (>30 days)	After thrombosis (<90 days)	P	Clinically relevant change
Total score	Mean (SD)	Mean (SD)	...	%
Physical domain	Mean (SD)	Mean (SD)	...	%
Pain	Mean (SD)	Mean (SD)	...	
Bleeding	Mean (SD)	Mean (SD)	...	
Swelling	Mean (SD)	Mean (SD)	...	
Bruising	Mean (SD)	Mean (SD)	...	
Social functioning domain	Mean (SD)	Mean (SD)	...	%
Daily activities	Mean (SD)	Mean (SD)	...	
Appearance	Mean (SD)	Mean (SD)	...	
Sleep	Mean (SD)	Mean (SD)	...	
Bathing and showering	Mean (SD)	Mean (SD)	...	
Dialysis complications domain	Mean (SD)	Mean (SD)	...	%
Problem on dialysis	Mean (SD)	Mean (SD)	...	

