Access care	Mean (SD)	Mean (SD)	...	
Hospitalization	Mean (SD)	Mean (SD)	...	
Worry about access longevity	Mean (SD)	Mean (SD)	...	

Compare SF-VAQ scores before (latest but >30 days before) and after (earliest but <90 days after) the thrombosis. Calculate the proportion of patients with a clinically relevant change in SF-VAQ scores. The clinically relevant change in SF-VAQ scores is defined as 0.5 times the standard deviation of the difference in SF-VAQ scores between two adjacent measurements in patients without vascular access-related interventions or vascular access-related (serious) adverse events.

Statistical analysis: paired Student t-test

Table 5E: Predictors of SF-VAQ scores at baseline

	Total score		Physical domain		Social domain		Complications domain	
	β (95% CI)	P	β (95% CI)	P	β (95% CI)	P	β (95% CI)	P
Sex (male)								
Age (/year)								
Body mass index (/kg/m ²)								
Diabetes mellitus (yes)								
Dialysis treatments per week								
Vascular access type								
Arteriovenous fistula								
Radiocephalic fistula								
Brachiocephalic fistula								
Brachiobasilic fistula								
Arteriovenous graft								
Age vascular access (/month)								
Previous vascular access								
Previous vascular access interventions								
Baseline access flow (/100 mL/min)								

Groups are based on initial randomization. Include only questionnaires with complete data.

Statistical analysis: all variables will be entered into multivariable linear regression models

Check for assumptions of statistical model: linearity, multicollinearity, and independence of errors

Table 6A: Repeatability / Test-retest reliability of ultrasound dilution flow measurements

	Point estimate	95% CI
Standard error of measurements (SEM)		
Coefficient of variation (CV)		

Same observer under the same conditions using the same measurement instrument (test-retest)

Include all ultrasound dilution flow measurements with 3 replicates (N=...)

Check for assumptions of statistical model: normal distribution of measurements and homogeneity of variance within subjects

Table / Figure 6B: Reproducibility / Inter-session reliability of ultrasound dilution flow measurements

Without correction for blood pressure

	N	Bias	Limits of agreement
Flow measurements within 2 weeks			
All measurements		mL/min	mL/min
Only random controls		mL/min	mL/min
Flow measurements within 1 week			
All measurements		mL/min	mL/min
Only random controls		mL/min	mL/min

With correction for blood pressure

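### The SF-VAQ cutoff for clinically relevant change lies inside event-free variability, and Tables 5C and 5D give no direction and no event-free comparison

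*SAP*

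**What the plan says.** The definition stands under Table 5C (change with interventions) and again under Table 5D (change with thrombosis), in section 6 of the SAP. In both, the clinically relevant change is "defined as 0.5 times the standard deviation of the difference in SF-VAQ scores". The reference group is given in the same sentence: the difference is taken "between two adjacent measurements in patients without vascular access-related interventions or vascular access-related (serious) adverse events". The SD is therefore that of the change score in event-free patients, not that of the score at one time point.

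The cutoff is then applied to individuals: "Calculate the proportion of patients with a clinically relevant change in SF-VAQ scores". Each table has one percentage column for this, filled for the total score and the three domain scores. No direction is given. Neither table has a column for event-free patients. The other columns hold the mean and SD before and around or after the event, with a paired t-test.

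Section 5.1.2 gives the spacing: "SF-VAQ measured at baseline and every 3 months during the follow-up period". The table notes give the scoring, from items rated 1 to 7: "Domain scores are the sum of the 4 questions. The total score is the sum of the 3 domains".

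**The concern.** A responder percentage can be read only if the reader knows what it would be without the event. Here the cutoff is a fixed fraction of the event-free spread, so a sizeable share of event-free patients must lie beyond it. A reader who sees that some 60% of patients had a clinically relevant change after thrombosis would probably credit the thrombosis, although much the same figure could arise with no effect. The unstated direction makes this worse: patients who improved and patients who worsened may be added together.

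At stake is the interpretation of two descriptive tables on a named secondary outcome measure.

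**Working it through.** The SAP states no SD, no numeric cutoff and no expected percentage, so there is no figure of its own to reproduce. The check asks what the rule gives when the event has no effect.

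**Inputs from the SAP.** Multiplier 0.5; SD of the adjacent-measurement difference in event-free patients; application to individuals; direction not stated; integer scores.

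**Assumption for the base case.** Event-free change D is normal with mean 0 and SD s. With no effect, change around an event follows the same distribution.

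**Base case.** The cutoff is 0.5s.
- One given direction: P(D > 0.5s) = 1 − Φ(0.5) = 0.309.
- Either direction: 2 × (1 − Φ(0.5)) = 0.617.

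The size of s cancels, so a more or less precise instrument gives the same result. The shape of the distribution does not cancel.

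**Other shapes, either direction.**

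| Event-free change | Share beyond 0.5 SD |
|---|---|
| Normal, mean 0 | 61.7% |
| Normal, mean drift of 0.1 to 0.3 SD | 61.9% to 63.3% |
| Rounded to integers, SD 2 to 12 points | 45% to 62% |
| t distribution, 10 down to 3 df | 59% down to 45% |
| Laplace, exp(−0.5√2) | 49% |
| 10% to 50% exact zeros, the rest normal | 57% down to 36% |

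For the last row, with a share q of zeros and overall SD 1, the formula is (1 − q) × 2 × (1 − Φ(0.5√(1 − q))). At q = 0.5 it gives 0.362. For the symmetric shapes the share in one direction is half of these values, so at the low end 36% / 2 = 18%.

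**How well the percentage separates effect from no effect.** Take a true mean worsening of 0.5s, with normal change.
- Either direction at 0.5s: 1 − Φ(0) + Φ(−1) = 0.500 + 0.159 = 65.9%, against 61.7% with no effect, a rise of 4.2 points.
- Worsening only at 0.5s: 1 − Φ(0) = 50%, against 30.9%, a rise of 19.1 points.
- Either direction at 1.96s: 7.9%, against 5.0%.
- Worsening only at 1.96s: 1 − Φ(1.46) = about 7%, against 2.5%.

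Pooling the directions removes most of the contrast. Splitting them, with the event-free figure alongside, restores much of it at the cutoff the SAP already uses.

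**The case against.** The strongest reply is that these are within-patient descriptive tables, not comparisons of the randomised arms. Each row also carries the means and a paired t-test, so a null mean effect would show next to the percentage. Patient-reported outcomes are analysed by generalized estimating equations (sections 2.4 and 5.3), which do not use the cutoff. All of this stands and limits the consequence. It does not make the percentage itself interpretable.

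A reader might also go further than the SAP allows, in three ways.

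- **That a majority would always be labelled as changed.** The 62% needs both directions counted and near-normal change. The SAP states no direction, and counting worsening only is a plausible reading for a thrombosis table; the figure is then about 31%. SF-VAQ scores are integer sums on which exact zero changes are possible, so even the either-direction share can fall below half.
- **That these patients are unchanged and the rule misclassifies them.** The reference group is event-free, which is not the same as unchanged. Questionnaires are three months apart, and section 5.1.2 sets aside grade 1 complications as not relevant to the trial. Real shifts in satisfaction can occur, so the SD mixes measurement error with natural fluctuation. What does follow is that such change cannot be credited to an intervention or thrombosis.
- **That 1.96 SD should replace 0.5 SD as the threshold of clinical relevance.** The larger multiple marks change beyond background variability. It does not say what matters to patients, and it picks up far fewer true worsenings, as the last line of the check shows.

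**Conclusion.** The point holds as one of interpretation. Followed as written, Tables 5C and 5D would label a substantial share of patients as relevantly changed even if the event had no effect: about 31% if one direction counts and about 62% if both do, for roughly normal change centred on zero. Departures from normality put the either-direction share at roughly 36% to 62%. The SAP gives neither the direction nor the event-free percentage needed to read the result.

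The size rests on an assumed distribution, since the SAP gives no SF-VAQ change data. The qualitative conclusion does not depend on normality: under every shape examined, more than a third of event-free patients lie beyond the cutoff when both directions count. The issue does not reach the primary or safety analyses.

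**What to change.** In both tables:

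1. Report worsening and improvement in separate columns, and state which sign of the score difference is which.
2. Beside the event percentages, show the same two percentages for adjacent questionnaire pairs in event-free patients, for the total score and each domain.
3. Optionally, add a column based on 1.96 times the same SD, labelled as change beyond measurement variability (smallest detectable change) and not as clinically relevant. Under normality about 2.5% of event-free patients exceed it in each direction.

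The 0.5 SD definition can stay if the first two items are adopted, because the comparison then shows what it yields without an event. The cost is a few lines of SAP wording and a small number of extra columns, from data already needed to compute the SD. No new data collection is required. The change is best made before the analysis is run.

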2.7. Timing of outcome assessments

Physical examination of the vascular access will be done at each dialysis session. Volume measurements by ultrasound dilution will be done every month. Duplex ultrasound examination of the vascular access will take place in case of flow dysfunction, and interventions for flow dysfunction are part of standard clinical care for hemodialysis patients. Subjects enrolled in the trial will be asked to fill out questionnaires (SF-VAQ, EQ-5D-5L, MCQ and PCQ) at baseline and every 3 months until 24 months of follow up.

3. Statistical Principles

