Monitoring reports ^a person-years person-years
Flow measurements person-years person-years

Table 2G: Vascular access dysfunction detected by monitoring and surveillance - Monitoring reports

	Monitoring (... reports)	Surveillance (... reports)	P
Clinical indicators of flow dysfunction	%	%	...
Physical examination	%	%	...
Weak or discontinuous thrill	%	%	...
High pitched or discontinuous bruit	%	%	...
Hyperpulsatile vascular access	%	%	...
Weak vascular access	%	%	...
No thrill or bruit	%	%	...
Recurrent problems during dialysis	%	%	...
Inability to achieve target blood flow	%	%	...
New cannulation problems	%	%	...
Prolonged bleeding	%	%	...
Unexplained fall in dialysis efficiency	%	%	...
Other findings at inspection			
Aneurysm	%	%	...
Hand ischemia	%	%	...
Infection	%	%	...
Edema	%	%	...
Skin lesions	%	%	...
Hematoma	%	%	...

Statistical analysis: Chi squared tests.

Table 2H: Vascular access dysfunction detected by monitoring and surveillance - Surveillance flow measurements

	Monitoring (... measurements)	Surveillance (... measurements)	P
Access flow <500 mL/min ^b	%	%	...
With clinical indicators of flow dysfunction	%	%	...
Without clinical indicators of flow dysfunction	%	%	...
Access flow 500-1000 mL/min with >20% reduction from baseline ^c	%	%	...
With clinical indicators of flow dysfunction ^d	%	%	...
Without clinical indicators of flow dysfunction ^d	%	%	...

Data are presented as proportions. The sum of the proportions may not add up to 100% because patients may have more than one clinical indicator of flow dysfunction.

^a Monitoring reports were not transferred to the research database in two study sites (OLVG and MUMC+ from 11-2024 onwards) because of technical issues with the electronic patient files.

^b Access flow is considered <500 mL/min only when the initial low flow measurement was confirmed in a subsequent dialysis session.

^c Baseline is the first flow measurement after randomization.

[figure not shown]
^d Clinical indicators of flow dysfunction refer to the decision rules for interventions defined in the study protocol (used to send notifications to the study sites).

When counting flow measurements, only measurements for surveillance and confirmatory measurements after low flow are counted. Flow measurements to evaluate interventions or as random repeats are excluded from analysis.

[figure not shown]
Statistical analysis: Chi squared tests.

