	Loss of vascular access <30 days		No loss of vascular access <30 days		Total	
Access flow >500 mL/min	N	%	N	%	N	%
Access flow <500 mL/min	N	%	N	%	N	%
Total	N	%	N	%	N	100%

	Intervention for clinical indicators of flow dysfunction <30 days		No intervention for clinical indicators of flow dysfunction <30 days		Total	
Access flow >1000 mL/min or 500-1000 with <20% reduction from baseline	N	%	N	%	N	%
Access flow <500 mL/min or 500-1000 mL/min with >20% reduction from baseline	N	%	N	%	N	%
Total	N	%	N	%	N	100%
	Thrombosis <30 days		No thrombosis <30 days		Total	
Access flow >1000 mL/min or 500-1000 with <20% reduction from baseline	N	%	N	%	N	%
Access flow <500 mL/min or 500-1000 mL/min	N	%	N	%	N	%

1000 mL/min with >20% reduction from baseline						
Total	N	%	N	%	N	100%
	Loss of vascular access <30 days		No loss of vascular access <30 days		Total	
Access flow >1000 mL/min or 500- 1000 with <20% reduction from baseline	N	%	N	%	N	%
Access flow <500 mL/min or 500- 1000 mL/min with >20% reduction from baseline	N	%	N	%	N	%
Total	N	%	N	%	N	100%

	Intervention for clinical indicators of flow dysfunction <30 days		No intervention for clinical indicators of flow dysfunction <30 days		Total	
Mean dynamic venous pressure below threshold	N	%	N	%	N	%
Mean dynamic venous pressure above threshold	N	%	N	%	N	%
Total	N	%	N	%	N	100%
	Thrombosis <30 days		No thrombosis <30 days		Total	
Mean dynamic venous pressure below threshold	N	%	N	%	N	%
Mean dynamic venous pressure above threshold	N	%	N	%	N	%
Total	N	%	N	%	N	100%
	Loss of vascular access <30 days		No loss of vascular access <30 days		Total	
Mean dynamic venous pressure below threshold	N	%	N	%	N	%
Mean dynamic venous pressure above threshold	N	%	N	%	N	%
Total	N	%	N	%	N	100%

The analysis of diagnostic accuracy of vascular access surveillance is done in the monitoring study group. For diagnostic accuracy of vascular access surveillance to predict clinical signs of flow dysfunction, only measurements without clinical signs of flow dysfunction at the time of

measurement are included. [This leads to exclusion of the sites where clinical signs of flow dysfunction could not be uploaded].

Only flow measurements for surveillance and confirmatory measurements after low flow are included. Flow measurements to evaluate interventions or as random repeats are excluded from analysis. Baseline is the first flow measurement after randomization.

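### In the clinical-signs part of Table 6D, a bracketed note excludes whole sites without a time limit, although footnote a dates the missing monitoring reports from 11-2024 for at least one of the two sites

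*SAP*

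**What the plan says.** SAP section 5.1.2, item 6 (quality of the surveillance program), lists as a secondary outcome: "Diagnostic accuracy of vascular access flow volume measurements to predict clinical signs of flow dysfunction and access thrombosis within 1 month". Table 6D carries it out. Its notes fix three things:

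- The population: "The analysis of diagnostic accuracy of vascular access surveillance is done in the monitoring study group".
- An inclusion rule for prediction of clinical signs, under which "only measurements without clinical signs of flow dysfunction at the time of" measurement count.
- A bracketed remark on the consequence of that rule: "This leads to exclusion of the sites where clinical signs of flow dysfunction could not be uploaded".

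The missing data are described elsewhere. Footnote a, marked in Table 2F and printed below Table 2H, states: "Monitoring reports were not transferred to the research database in two study sites (OLVG and MUMC+ from 11-2024 onwards) because of technical issues". It places those issues in the patient record systems. Section 2.7 gives the measurement schedule: "Volume measurements by ultrasound dilution will be done every month".

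**The concern.** The inclusion rule and its stated consequence work at different levels. A rule about the state of the access at each measurement removes measurements where signs were present or where their presence is unknown. It does not remove a site for a period in which its reports reached the database. Footnote a indicates that at least one affected site has such a period.

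One analyst could follow the bracketed note and filter by site. Another could follow the rule and filter by record. They would report sensitivity, specificity and predictive values from different datasets. The site filter gives up eligible data in an analysis already confined to one study group, and it removes a whole centre for a fault that affected only part of its follow-up.

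**Working it through.** The SAP states no figure for this point, so there is none to reproduce. The check is a comparison of texts, followed by an illustration of size.

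**1. Which cross-tables are concerned.** Table 6D has three blocks: flow below 500 mL/min; flow below 500 mL/min or a reduction of more than 20% within 500-1000 mL/min; and mean dynamic venous pressure. Each block has three outcomes: intervention for clinical indicators of flow dysfunction, thrombosis, and loss of access. That makes 3 x 3 = 9 cross-tables. The rule and its note are tied to prediction of clinical signs, so 3 of the 9 are concerned.

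**2. Rule, note and footnote compared.** I take the sites in the bracketed note to be the two in footnote a, and I take a gap that starts at a date to mean that reports were transferred before it.

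| Measurements | Under the per-measurement rule | Under the bracketed note |
|---|---|---|
| Unaffected sites, no signs present | Kept | Kept |
| Affected site, reports not transferred | Cannot be classified, so not eligible | Dropped |
| Affected site, reports transferred, no signs present | Kept | Dropped |

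The two texts differ only in the last row.

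**3. The two readings of the date.**
- If 11-2024 belongs to the second-named site only (the natural reading), the first-named site has no reports at any time and drops out under either text. The last row then holds the second site's measurements before 11-2024.
- If the date governs both names, the last row holds earlier measurements at both sites.

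On either reading the last row is not empty if the site was measuring patients before 11-2024. No other text in the SAP limits the note to the period of the gap.

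**4. Size, for illustration only.** The SAP gives no number of sites, no patients per site and no site start dates.

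- Count of measurements = monitoring-group patients at the site x months before the gap x 1 per month. Assuming 10 to 40 patients and 6 to 24 months, this is 10 x 6 = 60 to 40 x 24 = 960, before removing measurements taken when signs were present.
- Share of all monitoring-group measurements = f / k, with k equal sites and a fraction f of one site's follow-up before the gap. Assuming k = 8 to 12 and f = 0.25 to 0.80, this is 0.25/12 = 2.1% to 0.80/8 = 10%.
- Gain relative to what remains after dropping two sites = f / (k - 2): 0.25/10 = 2.5% to 0.80/6 = 13.3%.
- Approximate narrowing of intervals = 1 - 1/sqrt(1 + gain): 1 - 1/sqrt(1.025) = 1.2% to 1 - 1/sqrt(1.133) = 6.1%.
- If the date governs both sites with the same f, the gain doubles, to between 5% and 26.7%.

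The narrowing is rough. It treats measurements as independent, whereas monthly measurements repeat within patients, and the precision of sensitivity depends on the number of events within 30 days. A small or late-starting site would fall below these ranges.

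**The case against.** The strongest reply is that the per-measurement sentence is the operative rule and the bracketed one a loose remark on its effect. An analyst could apply the rule, use the date in footnote a, and contradict no operative sentence. This has force: the SAP does not prove that eligible data will be discarded, only that they are discarded if the note is followed as written. But the note is the only text that says what happens to the affected sites, and it carries no date.

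Four stronger readings are tempting, and the SAP does not support them:

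- A reader might infer that Table 6D as a whole loses sites. The restriction opens with prediction of clinical signs, and the six cross-tables for thrombosis and access loss are not stated to lose any.
- A reader might infer that two centres are dropped needlessly. On the natural reading of footnote a, the first-named site has no reports to restore, and only one centre is at issue.
- A reader might infer bias. The gap is put down to technical issues with electronic files, which gives no reason to expect a link with outcome. The centre mix changes, but no direction of error can be shown.
- A reader might take the percentages above as findings. They rest wholly on assumed site numbers, sizes and timing.

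**Conclusion.** The point holds as a mismatch between a measurement-level rule and an undated site-level note, in three of the nine cross-tables of Table 6D. Taken literally, the note drops measurements from before 11-2024 that meet the rule, at one affected site on the natural reading of footnote a and at both on the other. This rests on two assumptions: that the note and footnote a refer to the same sites, and that reports were transferred before the gap began.

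The consequence is a modest loss of precision that cannot be quantified from the SAP. It touches part of one secondary outcome; the primary and safety analyses are unaffected. It is a minor improvement that is almost free, and worth making before the dataset is built.

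**What to change.** Replace the bracketed note under Table 6D with wording such as: *measurements at the affected sites taken during the period in which monitoring reports were not transferred are excluded from the analysis of clinical signs of flow dysfunction; measurements taken at those sites while reports were transferred are kept.* In footnote a, state the start of the gap separately for each site, so that it is clear whether 11-2024 applies to one or both.

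The exclusion should be tied to the affected sites and dates. A general requirement that every measurement has a monitoring report for its session would apply everywhere, and could newly remove measurements at unaffected sites where a single report is absent.

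The cost is one replaced sentence, a clarified footnote, and a filter by site and date instead of by site alone. It needs no new data and no change to the conduct of the trial. If a gain in data is reported to justify the change, it should be marked as illustrative unless it is counted from the database.
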